5.6.2 Secondary Study Endpoints

1. Patients treated with CBT-I will have significantly greater improvements in sleep continuity from baseline to post-treatment compared to patients not administered CBT-I.
2. Patients treated with CBT-I in combination with solriamfetol will have significantly greater improvements in sleep continuity from baseline to post-treatment compared to patients treated with CBT-I alone.
3. **Exploratory hypotheses:** Patients treated with CBT-I in combination with solriamfetol will have significantly greater adherence with sleep restriction (i.e., sleep rescheduling, prescribed time to bed [PTTB]) and on daytime performance measures (e.g., ESS, FSS, etc.) compared to CBT-I alone.

i. Primary Safety Endpoints [if applicable]

As noted above, side effects will be assessed in several ways: daily assessments via the sleep diaries, weekly evaluation with a medical symptom checklist (52 symptoms where positive endorsements allow subjects to rate their average severity and number of days affected).

6. Study Population and Duration of Participation

Subjects 25 to 65 years old (inclusive) and who have a stable sleep/wake schedule (no shift work) with a preferred sleep phase between 10:00 PM and 8:00 AM. The recruitment sample will be populated by 40 completed subjects. The study duration will be 12 weeks, with a one-time follow-up at 3 months post-treatment.

a. Inclusion Criteria

Participants will meet the diagnostic criteria for Insomnia Disorder according to Diagnostic and Statistical Manual of Mental Disorders (DSM-5). The complaint of disturbed sleep will meet the following criteria:

- ≥ 30 minutes to fall asleep (SL) and/or ≥ 2 awakenings per night of ≥ 15 minutes duration and/or wake after sleep onset (WASO) time of ≥ 30 minutes where total sleep time (TST) did not exceed 6 hours (unless sleep efficiency [SE] is $\leq 80\%$).
- The problem is present for ≥ 3 nights per week.
- The problem duration exceeds ≥ 6 months.
- The complaint of impaired daytime function must include, although not limited to, the report of daytime fatigue, sleepiness, or both.

Additional inclusion criteria are as follows.

1. Aged 25 to 65 years (inclusive).
2. Have a preferred regular sleep phase between 10:00 PM and 8:00 AM.

b. Exclusion Criteria

Please note that all subjects will have to receive physician assent before being enrolled into the study.

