As noted above, side effects will be assessed in several ways: daily assessments via the sleep diaries and weekly evaluation with a medical symptom checklist (52 symptoms where positive endorsements allow subjects to rate their average severity and number of days affected).

10. Statistical Plan

k. Primary Endpoint

The primary endpoint is total wake time (time spent awake in bed) at the end of post-treatment, as measured via a web based self-report Sleep Diary.

I. Secondary Endpoints

1. Patients treated with CBT-I will have significantly greater improvements in sleep continuity from baseline to post-treatment compared to patients not administered CBT-I.
2. Patients treated with CBT-I in combination with solriamfetol will have significantly greater improvements in sleep continuity from baseline to post-treatment compared to patients treated with CBT-I alone.
3. Exploratory hypotheses: Patients treated with CBT-I in combination with solriamfetol will have significantly greater adherence with sleep restriction (i.e., sleep rescheduling, prescribed time to bed [PTTB]) and on daytime performance measures (e.g., ESS, FSS, etc.) compared to CBT-I alone.

m. Sample Size and Power Determination

To detect a clinically significant difference in self-reported total wake time of 30 minutes between the four treatment groups at the end of post-treatment using an ANOVA test, this study will require 10 subjects per group x 4 groups = 40 treatment completers. These calculations assume a standard deviation in total wake time of 19 minutes, with 80% power to detect the clinically significant change at an alpha level of .05. A total of 60 subjects will be recruited to obtain a sample of 40 subjects that complete the study due to attrition.

n. Statistical Methods

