Primary analyses will be conducted on an intention to treat basis and the trial conducted and reported according to CONSORT guidelines. Variable distributions will be examined to investigate homoscedasticity, outliers and normality, and corrected where appropriate using data transformations. The primary analysis is a 4(condition: +/- solriamfetol and +/- CBT-I) x 2(time: pre- and post-treatment) mixed ANOVA on absolute and percent change in total wake time ([TWT], time spent awake per night). If the interaction between condition and time is significant, Dunnett multiple comparisons will be conducted to further investigate differences in TWT between active treatment conditions versus the control condition to test Hypotheses 1-3. These analyses will be unadjusted in the first instance and then adjusted for covariates (primarily, age and sex).

An interim unadjusted analysis as per above will be conducted after 50% of the target sample have completed post-treatment (i.e., when N=20).

Secondary analyses include examining the interaction between treatment condition and time on other outcomes, including sleep continuity assessed via Sleep Diary (SL, WASO, EMA, TST, SE), insomnia (ISI), daytime sleepiness (ESS and KSS), fatigue (FSS and modified KSS), and daytime function (FOSQ-10, POMS, and PVT). Additionally, compliance to the medication (adherence to daily pill administration, as assessed via blister packs) and to sleep restriction (adherence to prescribed time to bed) will be investigated as covariates.

i. Baseline Data

Baseline and demographic characteristics will be summarized by standard descriptive statistics (including mean and standard deviation for continuous variables such as age and standard percentages for categorical variables such as gender).

ii. Pharmacokinetic Analysis **N/A**

iii. Interim Analysis **N/A**

iv. Safety Analysis

Side effects and adverse events will be assessed in several ways: daily assessments via the sleep diaries, and with a weekly evaluation using a medical symptoms checklist (52 symptoms where positive endorsements allow subjects to rate their average severity and number of days affected),

An adverse event will be defined as 1) any behavioral or health complaint spontaneously reported during the study, 2) an above threshold score on the study clinical assessment instruments (ESS, PHQ-9, or GAD-7), and/or a 20% increase in the medical symptom check list scores (frequency or severity).

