o. Subject Population(s) for Analysis

- All-randomized population.
- All-treated population
- Protocol-compliant population

11. Safety and Adverse Events (as stated in the IRB template)

p. Definitions

i. Adverse Event

An adverse event (AE) is any symptom, sign, illness or experience that develops or worsens in severity during the course of the study. Illnesses or injuries will be regarded as adverse events. Abnormal results of diagnostic procedures are considered to be adverse events if the abnormality:

- results in study withdrawal
- is associated with a serious adverse event
- is associated with clinical signs or symptoms
- leads to additional treatment or to further diagnostic tests
- is considered by the investigator to be of clinical significance

ii. Serious Adverse Event

Serious Adverse Event

Adverse events are classified as serious or non-serious. A serious adverse event is any AE that is:

- fatal
- life-threatening
- requires or prolongs hospital stay
- results in persistent or significant disability or incapacity
- a congenital anomaly or birth defect
- an important medical event

Important medical events are those that may not be immediately life threatening but are clearly of major clinical significance. They may jeopardize the subject and may require intervention to prevent one of the other serious outcomes noted above. For example, drug overdose or abuse, a seizure that did not result in in-patient hospitalization, or intensive treatment of bronchospasm in an emergency department would typically be considered serious.

All adverse events that do not meet any of the criteria for serious should be regarded as **non-serious adverse events**.

q. Recording of Adverse Events

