At each contact with the subject, the investigator will seek information on adverse events by specific questioning and, as appropriate, by examination. Information on all adverse events will be recorded immediately in the source document, and also in the appropriate adverse event module of the case report form (CRF). All clearly related signs, symptoms, and abnormal diagnostic procedures results will be recorded in the source document, though grouped under one diagnosis. All adverse events occurring during the study period will be recorded. The clinical course of each event will be followed until resolution, stabilization, or until it has been determined that the study intervention or participation is not the cause. Serious adverse events that are still ongoing at the end of the study period will be followed up to determine the final outcome. Any serious adverse event that occurs after the study period and is considered to be possibly related to the study intervention or study participation will be recorded and reported immediately.

r. Relationship of AE to Study

The relationship of each adverse event to the study procedures will be classified in terms of the event's potential relationship to the study (definitely related, probably related, possibly related, unlikely or unrelated).

s. Reporting of Adverse Events, Adverse Device Effects and Unanticipated Problems

The occurrence of adverse events will be reported to the study's medical collaborators, advisory board chair, Penn IRB, and our contacts at Axsome.

If the report is supplied as a narrative, the minimum necessary information to be provided at the time of the initial report includes:

- *Study identifier*
- *Study Center*
- *Subject number*
- *A description of the event*
- *Date of onset*
- *Current status*
- *Whether study intervention was discontinued*
- *The reason why the event is classified as serious*
- *Investigator assessment of the association between the event and study intervention*

Additionally all other events (unanticipated problems, adverse reactions, unanticipated adverse device effects and subject complaints) will be recorded and reported with respect to institutional and federal policies as described in the Penn Manual and below.

i. Follow-up report

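### Section 10.n.iv counts above-threshold scores and 20% checklist rises as adverse events with no stated baseline condition, which conflicts with Section 11.p.i, and its GAD-7 trigger is never scheduled on study

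*Combined protocol and SAP*

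**What the plan says.** Section 10.n.iv (Safety Analysis) lists three routes to an adverse event:

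- a spontaneous complaint: "any behavioral or health complaint spontaneously reported during the study";
- a scale score: "an above threshold score on the study clinical assessment instruments (ESS, PHQ-9, or GAD-7";
- a checklist change: "a 20% increase in the medical symptom check list scores (frequency or severity".

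No threshold is given for any of the three scales anywhere in the document. The checklist rule does not say whether the rise is measured from the pre-treatment score, the placebo run-in or the previous week.

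Section 11.p.i gives a second definition: "any symptom, sign, illness or experience that develops or worsens in severity during the course of the study". Nothing says which of the two governs the safety analysis.

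Three other places bear on this:

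- Section 6.a: the daytime complaint needed for entry "must include, although not limited to, the report of daytime fatigue, sleepiness, or both".
- Table of Instruments (Section 8.g): the checklist, ESS and PHQ-9 are marked Pre, Weekly and Post. GAD-7 is not in the table; its only other mention is as an eligibility tool in Section 6.b.
- Section 11.s: adverse events go to the medical collaborators and to the "advisory board chair, Penn IRB, and our contacts at Axsome".

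**The concern.** An adverse event is normally something that appears or gets worse after baseline. The score rule in Section 10.n.iv is a test of level, not of change. Because entry requires fatigue or sleepiness, some participants may already be above whatever ESS cut-off is used, and ESS is repeated weekly. Such a person can be recorded as having an event although nothing has changed.

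The checklist rule is a test of change, but a purely relative one. It is undefined from a score of zero, and from a low score one extra symptom satisfies it. Weekly repetition gives ordinary fluctuation many chances to cross the line.

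At stake is the content of the reports that go to the board chair, the IRB and the funder, and the meaning of any later count of participants with at least one event.

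**Working it through.** **The plan's own figure.** The safety section states none. The sample size in Section 10.m fixes the arm sizes. With two groups 30 minutes apart and two midway, f = √[(15² + 15²)/4]/19 = 10.61/19 = 0.558. At alpha 0.05 this needs 10 per group (power 81.1%), which agrees with the plan. Pooled over CBT-I, that is 20 on drug and 20 on placebo.

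**Step 1: the two definitions applied to the same participant.**

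| Participant | Section 10.n.iv | Section 11.p.i |
|---|---|---|
| Above ESS threshold at Pre, unchanged | event | not an event |
| Below at Pre, crosses later | event | event |
| Above at Pre, then worse | event | event |
| Above at Pre, improves but still above | event | not an event |

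The definitions disagree in the first and fourth rows. The number of participants in those rows cannot be worked out: no cut-off is given, no ESS minimum is set for entry, and fatigue without sleepiness is enough to qualify.

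**Step 2: GAD-7.** The rule needs an on-study score. The Table of Instruments provides none, so the trigger cannot fire.

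**Step 3: the 20% rule when nothing changes.** From the documents: 8 weekly checklists during treatment (Section 4) and one Pre score. Assumed: baseline and weekly totals are independent draws from one distribution, and a participant is flagged if any week is above baseline and at least 1.2 × baseline. Simulation of 400,000 participants:

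| Assumed score | Flagged at least once |
|---|---|
| Normal, CV 5% | 3% |
| Normal, CV 7% | 14% |
| Normal, CV 10% | 33% |
| Normal, CV 30% | 71% |
| Poisson, mean 200 | 15% |
| Poisson, mean 100 | 35% |
| Poisson, mean 40 | 56% |
| Poisson, mean 2 | 83% |

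At Poisson mean 2, 13.5% of baselines are zero (e⁻²); leaving them out still gives 80%.

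The rule is met by frequency or severity, which is two scores. A log-normal model with two scores correlated 0.5 (assumed) flags 5.5%, 53% and 89% at CV 5%, 10% and 30% with baseline as reference. With the previous week as reference it flags 7%, 81% and 100%. The unnamed reference therefore matters, and naming baseline does not by itself remove the noise.

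**Step 4: what this does to a pooled count.** If a share b is flagged by noise in both arms, independently of a true drug excess d, the drug arm shows 1 − (1 − b)(1 − d), so the difference is d(1 − b). At b = 3% the difference keeps 97% of its size; at b = 83% it keeps 17%. For the protocol's own placebo-adjusted headache excess of up to 5% (Section 14.dd), exact Fisher power with 20 v 20 is 0.3% at b = 0 and at most 2.9% at any b tried from 0% to 90%.

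**Step 5: whether item-level counting would be better.** Calling any one of the 52 items an event when it worsens gives 52 × 8 = 416 looks per participant. At an assumed false-worsening rate per item-week of 0.1%, 0.2% or 0.5%, 1 − (1 − p)⁴¹⁶ = 34%, 57% or 88% of unchanged participants are flagged. That is not shown to improve on the 20% rule.

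**The case against.** The strongest reply is that the sections can be read together, with Section 11 as the general definition and Section 10.n.iv as screening triggers. A 20% increase implies some reference, and Pre scores exist. Over-inclusive capture is also a defensible choice in a small trial whose publication plan gives effect-size data as its main purpose. Part of this stands: the checklist defect is an unnamed reference and a missing minimum, not the absence of any reference. The rest does not remove the conflict. Section 10.n.iv is worded as the definition of an adverse event, and the document nowhere calls its criteria triggers for review under Section 11.

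Stronger readings are tempting and should not be drawn.

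- A reader might infer that the rule hides any drug signal. It does not. Each checklist entry is rated separately ("weekly evaluation with a medical symptom checklist (52 symptoms where positive endorsements allow subjects to rate their average severity and number of days affected"), and diary side effects, spontaneous complaints, serious events and the relatedness classification all remain.
- A reader might infer that a planned between-arm test is compromised. Section 10.n.iv specifies no pooled comparison, so dilution applies only if one is made. For the excess rates the protocol quotes, the small sample is the main limit with or without the fix.
- A reader might infer that most participants will be falsely flagged. That depends on variability that the documents do not report; at CV 5% the figure is about 3%.
- A reader might infer a bias against placebo or CBT-I, because ESS is also an efficacy outcome and Section 14.cc expects temporary sleepiness with CBT-I. This is possible, but without a cut-off or baseline scores it cannot be shown or sized. Sleepiness that truly worsens is an event under Section 11.p.i as well.

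**Conclusion.** The point holds as a conflict and a gap in definition. Followed as written, Section 10.n.iv records an event for an unchanged participant who entered above threshold, which Section 11.p.i would not. It also applies a 20% rule that cannot be computed without a choice the plan does not make, and it includes a trigger with no data behind it. These findings need no assumptions.

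The size does. Testing one total score against baseline, the share of unchanged participants flagged runs from about 3% (normal, CV 5%) to 83% (Poisson mean 2). The number affected by the ESS rule is unknown. The consequence is non-events in the safety reports and dilution of a pooled any-event count if one is made. It is worth correcting, but it does not touch the primary efficacy analysis or the handling of serious events.

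**What to change.** - State that Section 11.p.i governs, and rewrite Section 10.n.iv to agree with it.
- For ESS and PHQ-9, name the threshold. Count an event only when a score below it at the pre-treatment assessment crosses it, or a score above it worsens by a pre-stated number of points.
- For the checklist, name the pre-treatment score as the reference and add a minimum absolute change to the 20% rule. This handles zero and low baselines. The minimum has to be set with the scale in mind: from a score of 40, 20% is already 8 points, so a minimum below 8 changes nothing there.
- Tabulate by arm the individual symptoms that are new or worse than pre-treatment, without making a single-item change an event in itself.
- Remove GAD-7 from the rule, or add it to the weekly and post-treatment schedule.

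The cost is protocol wording, since the Pre scores for ESS, PHQ-9 and the checklist are already collected. Keeping GAD-7 would add one questionnaire to the schedule. The downside is slightly less inclusive capture of adverse events, which the symptom table partly makes up for.

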All study medication will be provided by Axsome Pharmaceuticals (no cost) and will be received, stored, and packaged by the University of Pennsylvania Investigational Drug Service (IDS). IDS will create blister packs for each patient that are identical and will allocate active medication and placebo according to treatment condition. This will enable double blinding of the study. All doses will be over-encapsulated, and all daily doses will be delivered as a single capsule. The use of blister

packs will also allow us to not only track adherence but to identify the patterning of medication use. Blister packs will be returned once a month when subjects will be evaluated and provided the next month's medication supply. The study CRC will dispense and receive the foil packs. The pattern of used and unused data will be coded.

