3.2 Secondary Objectives (if applicable)

Assess the effects of solriamfetol on daytime sleepiness, fatigue, adherence with “sleep rescheduling”, and on daytime performance

4. Investigational Plan

All subjects will be monitored for 2 weeks prior to treatment, for 8 weeks during treatment, and for 2 weeks following treatment. Additionally, subjects will complete two questionnaires complete two questionnaires (Insomnia Severity Index [ISI] and Retrospective Sleep Continuity Assessment Questionnaire [RSCAQ]) 3 months after completing treatment.3 months after completing treatment. Subjects receiving solriamfetol will take medication at 2pm daily for 4 weeks. Medication use will also include a 1-week placebo run-in and a 3-week placebo “run-out” (8 weeks’ total). Note: This design was used for our prior trials of CBT-I with wake promoting medications. Subjects receiving CBT-I will have 8 weekly

sessions (up to 90 minutes in duration). Daily sleep diaries will be administered to assess for differences in sleep continuity between conditions and over time. Self-report weekly assessments will also be administered and will include standard retrospective measures of insomnia (ISI), sleepiness (Epworth Sleepiness Scale, ESS), depression (PHQ-9), fatigue (Functional Assessment of Chronic Illness Therapy – Fatigue Scale [*FACIT-Fatigue*]), PROMIS-Short Form 7a, and Brief Fatigue Inventory [BFI]), treatment acceptability (MITAS)), and daytime function (Functional Outcomes of Sleep-10 item, FOSQ-10). Daytime function will also be objectively assessed daily via Ecological Momentary Assessment and at the end of baseline treatment, and post treatment periods using a PVT phone-based app. Self-report assessments will be accomplished on-line via RedCap software and subjects will also be asked to complete weekly and monthly questionnaires via Hypknowledge (a PHT Penn Health Tech Clinical Research Tool) site.

Treatment Regimen (as noted above)

The first five participants will be enrolled slowly to observe whether any adverse responses occur (e.g., taking longer to fall asleep after medication administration at 2pm) that would necessitate protocol modifications, for instance to the timing of medication dosing, if not amount.

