Session 2: data acquisition and delivery of sleep restriction therapy & stimulus control instructions

Session 3: review of sleep hygiene

Session 4: management of non-adherence and/or time-in-bed titration only

Session 5: cognitive therapy [de-catastrophization]

Session 6: management of non-adherence and/or time-in-bed titration only

Session 7: management of non-adherence and/or time-in-bed titration only

Session 8: review of treatment progress and relapse prevention.

All treatment will be delivered by a single master therapist ([name] PhD CBSM). [name] has more than 27 years’ experience with CBT-I, he is one of the authors of our published treatment manual (1), and he is also a co-author of a second CBT-I treatment manual (2). He was a consultant for the VA’s rollout of CBT-I, he jointly conducts the Penn 3-day Basic and Advanced CBT-I courses, and he regularly conducts on-site one-day CBT-I workshops. As a final testament to his expertise, he was one of the first individuals to be certified in behavioral sleep medicine and one of the first to receive the SBSM’s Distinguished Career Achievement Award.

5. General Design

A double blind 2x2 mixed model design. The two factors will be 1) treatment (+/- solriamfetol and +/- CBT-I) and 2) Time (pre-post assessment, with additional follow-up data). Patients with insomnia will be randomly assigned to treatment condition.

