The study CRC will dispense and receive the foil packs. The pattern of used and unused medication will be captured by xeroxing or photographing each foil pack. Once a subject has completed their participation in the study (i.e., they have either completed the study, experienced treatment non-response or relapse, or withdrew from the study) they will be given the option to either (a) come to our office at [name] and return the blister packs to the CRC, who will bring them to IDS for destruction or (b) take the blister-packs to a local pharmacy and record a video of themselves placing the blister-packs in a safe drug disposal box, and share the video with study staff. This can be done via email or by uploading the video via REDCap (see example link: <https://redcap.med.upenn.edu/surveys/?s=XE4T3MKRTPNL7JY7>). The video will not include the subject's face or other identifying information. This will ensure that the medication is properly disposed of, and that this disposal is documented. Note: the study's informed consent already mentions that we cannot guarantee the security of email correspondence, and that email privacy is based on the email provider's user agreement. We will remind subjects of this so they can consider this factor when deciding whether to return the medication to our office (no video required) or to their local pharmacy's drug disposal box (video required).

h. Subject Compliance Monitoring

Pill use will be tracked per week via the sleep diary. These data will be compared to, and corroborated with, the foil pack data.

i. Return or Destruction of Investigational Product

Blister packs will be returned once the subject has completed the study. Following the archiving of the pill pack (pill utilization pattern captured by xeroxing or photograph) the study CRC will return the foil packs and remaining capsules to Investigational Drug Services of the University of Pennsylvania for destruction.

8. Study Procedures

All subjects will receive medication and complete daily sleep diaries and weekly questionnaires.

Does your study use MRI? (CAMRIS is the appropriate contact for all studies involving MRIs)

Yes No

Check of all that apply:

1.5T MRI
 3T MRI
 7TMRI

Does the MRI use investigational sequences and/or coils?

(See Experimental Device Clause)

Yes No Unsure

Does your study include pregnant women?

(See Pregnancy Clause and Justification)

Yes No

Does the MRI require the use of Contrast Agents?

(See Contrast Risks)

Yes No

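### Adverse events are sought at each contact, and scheduled contacts depend on CBT-I status, so event counts can differ between arms with and without CBT-I apart from any true effect

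*Combined protocol and SAP*

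**What the plan says.** Section 11.q (Recording of Adverse Events) ties questioning to contact: "At each contact with the subject, the investigator will seek information on adverse events by specific questioning". It gives no schedule of contacts and asks that all adverse events in the study period be recorded.

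Contact is laid down unevenly elsewhere:

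- Section 4 (Investigational Plan): "Subjects receiving CBT-I will have 8 weekly" sessions of up to 90 minutes, held individually by video link. No matching sessions or calls are described for the arms without CBT-I.
- Section 2, for all arms: "Blister packs will be returned once a month when subjects will be evaluated and provided the next month's medication supply".
- Section 7.i, also for all arms: "Blister packs will be returned once the subject has completed the study". This does not agree with the monthly return in section 2.

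Section 10.n.iv (Safety Analysis) names two routes of assessment, the daily sleep diary and a weekly 52-symptom checklist. Section 8 gives diaries and weekly questionnaires to every subject. The definition of an adverse event in 10.n.iv starts with "any behavioral or health complaint spontaneously reported during the study". It then adds above-threshold scores on the ESS, PHQ-9 or GAD-7 and a 20% rise in the checklist score. Nothing says that events will be tabulated by how they came to light.

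**The concern.** How often a subject is asked about adverse events, or has a live occasion to mention one, is fixed in part by randomised arm. A mild complaint that would go unrecorded in a subject without CBT-I may be recorded in a subject who sees a therapist that week. Once recorded, it enters the same total as events from the diary and checklist.

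The comparisons exposed are those that cross CBT-I status: combination against solriamfetol alone, CBT-I alone against solriamfetol alone, CBT-I alone against placebo alone, and the pooled contrast of CBT-I against no CBT-I. The first two bear on the rationale in section 1, where solriamfetol is put forward as an alternative for patients who do not tolerate sleep restriction. Section 14.cc expects CBT-I itself to cause temporary fatigue and sleepiness. If sources are not kept apart, a true effect of that kind cannot afterwards be told from an effect of more frequent asking.

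**Working it through.** The plan states no figure on this point, so there is none to reproduce. The check has three steps.

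**1. Scheduled live contacts.** The observation period comes from section 4: "All subjects will be monitored for 2 weeks prior to treatment, for 8 weeks during treatment, and for 2 weeks following treatment". One evaluation every four weeks is taken from section 2. The lower CBT-I count supposes that monthly evaluations coincide with sessions; the higher supposes that they are separate.

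| Period | Without CBT-I | With CBT-I | Ratio |
|---|---|---|---|
| 8 treatment weeks | 8/4 = 2 | 8 to 8 + 2 = 10 | 4.0 to 5.0 |
| All 12 weeks | 12/4 = 3 | 8 to 8 + 3 = 11 | 2.7 to 3.7 |

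Under section 7.i the arms without CBT-I would have fewer contacts and the gap would be wider.

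**2. Which contrasts are affected.** Solriamfetol alone and placebo alone have the same schedule, as do the combination and CBT-I alone. Solriamfetol against placebo is therefore balanced within each CBT-I stratum. It is also balanced when pooled, with the equal groups of 10 in section 10.m. Only contrasts across CBT-I status are unbalanced.

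**3. From contacts to recorded events.** The contact ratio is not the event ratio, because the diary and checklist catch events equally in all arms. Let *s* be the probability that an event is caught by the diary or checklist and *q* the probability that live questioning catches it, the two acting independently. Then

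P(recorded) = 1 − (1 − *s*)(1 − *q*).

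Neither *s* nor *q* is in the documents; both are assumptions, shown as a range. True event rates are taken as equal. Monthly questioning is first assumed to elicit half as much as weekly, with *q* (weekly, monthly) of (0.5, 0.25) or (0.8, 0.4).

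| *s* | *q* = 0.5 vs 0.25 | Ratio | *q* = 0.8 vs 0.4 | Ratio |
|---|---|---|---|---|
| 0 | 0.50 / 0.25 | 2.0 | 0.80 / 0.40 | 2.0 |
| 0.5 | 0.75 / 0.625 | 1.20 | 0.90 / 0.70 | 1.29 |
| 0.8 | 0.90 / 0.85 | 1.06 | 0.96 / 0.88 | 1.09 |
| 0.9 | 0.95 / 0.925 | 1.03 | 0.98 / 0.94 | 1.04 |

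Worked cell, *s* = 0.5 and *q* = 0.8 vs 0.4: 1 − 0.5 × 0.2 = 0.90; 1 − 0.5 × 0.6 = 0.70; 0.90/0.70 = 1.29. Of ten true events in each arm, nine would be recorded with CBT-I and seven without.

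If monthly questioning elicits as much as weekly (*q* = 0.8 in both), the two probabilities are equal and the ratio is 1.0 at every *s*.

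**The case against.** The best reply is that the safety assessment is already equal. Section 10.n.iv names only the diary and the checklist as routes of assessment, every subject completes both, and a checklist rise or a high questionnaire score makes an event with no live contact. This stands as far as size is concerned: a reader who infers from a four- to five-fold contact ratio that event counts will differ several-fold goes beyond the documents. It does not close the gap. Section 11.q adds a live route, 10.n.iv counts spontaneous complaints, and a symptom that moves the checklist score by less than 20% can still become an event if it is mentioned in a session.

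A second reply is that section 11.q speaks of the investigator, whereas section 4 says "All treatment will be delivered by a single master therapist". That sessions count as contacts with questioning is an inference. But sections 2 and 4 count the therapist among the study staff who decide on dose timing, and section 11.s.ii has serious events reported to the therapist among others. Even if the therapist asks nothing, eight live sessions give more occasions for a spontaneous complaint. Specific questioning and spontaneous report are different routes, but both run through live contact.

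Third, no document caps contacts without CBT-I at two. Sections 8.d and 8.g allow unscheduled contact by phone, email and video, and changes in dose timing are not confined to the CBT-I arms. This stands: the counts above are of scheduled contacts only.

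Fourth, 10.n.iv specifies no four-arm event table and no between-arm safety test. This also stands. The harm arises only if events are shown by arm, which seems likely in a four-arm trial but is not written down.

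**Conclusion.** The point holds in a limited form. Live ascertainment of adverse events is unequal by CBT-I status, and the plan does not separate events by source, so counts can differ across CBT-I status apart from any true effect. The documents do not show that they will. On the stated assumptions the capture ratio runs from 1.0 to about 1.3 when the diary and checklist catch at least half of events. It reaches 2.0 only if they catch nothing. The result rests on CBT-I sessions serving as occasions for questioning or report, and on monthly evaluations being the only scheduled contact without CBT-I.

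Two stronger readings are not supported. A reader might infer that solriamfetol alone is the least observed arm and would look safest for that reason; placebo alone has the same schedule, so both arms without CBT-I share the thinner ascertainment. A reader might also infer that the drug's safety comparison with placebo is biased; it is balanced on contact frequency, both within CBT-I strata and pooled.

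**What to change.** In section 10.n.iv:

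- Base between-arm comparisons of non-serious adverse events on the daily diary and weekly checklist, which all arms complete on the same schedule.
- Add one open adverse-event item to the weekly online form for all arms.
- List events elicited at sessions or other contacts separately.
- Count serious adverse events from any source.

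Sections 2 and 7.i should be reconciled on when packs are returned and subjects evaluated, so that scheduled contact without CBT-I is known. Solriamfetol against placebo needs no special handling on this account.

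The cost is analysis wording and one item on an existing form. The downside is that headline counts leave out some mild events reported only at a contact; these are still recorded and listed.
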